2.9. Obtaining informed consent

At the screening visit, all patients will be given a detailed patient information sheet that includes the details of the trial and potential to participate in the trial. Once the biopsy results are known from the screening visit, patients will be written to with the test results. A leaflet explaining the study and recruitment details will be sent to the patient (in accord with GCP guidelines) along with the test results. The written informed consent will be sought at a subsequent visit by a senior member of the team who is trained in obtaining consent for clinical trial participation. The patients' GP will be informed by a letter of their patient's inclusion in the study. Copies of the informed consent will be stored in patient's clinical records.

2.10. Proposed time period for retention of documents

Trial documents will be retained for a 10 year period from final publication.

2.11. Proposed sample size

The trial is to be run in three phases: phase I is to pilot recruitment – we aim to recruit 75 patients in the first 6 months; phase II is to pilot follow-up –additionally, by the end of 12 months, we aim to have recruited a total of 165 patients. In phase III we aim to accelerate recruitment by adding more sites if necessary and to have recruited 400 by the end of year 2 and 660 by the end of year 3. The feasibility of these numbers will be shown in phases I and II.

The total of 660 has been chosen so as to provide 80%-90% power with follow-up until 6 years after the first patient is randomised under a number of scenarios consistent with published progression rates in untreated and minimally treated patients with AIN2/3 (about 11% after a median of 5 years) and published results of treated patients. In a 10-year experience study, patients with mostly extensive AIN 2/3 (81.2%) were treated with electrocautery and 3 (1.2%) developed anal cancer, but in our cohort no patient had anal cancer during 5 years (median) follow-up (0%).

The table below shows the power to detect a difference between the randomised arms at the 0.05=level using the two-sided log-rank test under a variety of scenarios after a maximum of 6 years follow-up. Throughout we assume that 10% of patients will be lost to follow-up in year 1, and 5% of those still in the trial will be lost in each subsequent year. These rates represent those who will stop coming to clinic. We anticipate close to 100% passive follow-up for anal cancer though flagging with the English Cancer Registry. We do not explicitly allow for surveillance-only patients receiving treatment, but we believe that the more modest hazard ratios (for intent to treat) would allow for a certain amount of treatment in the surveillance only arm. (Calculations were done in Stata using the command "artsurv").

We consider incidence rates in the surveillance only arm of 1.0%/year, 2.0%/ year and 2.5%/year and treatment effects of 90% (corresponding to a hazard ratio of 0.1), 80%, 65% and 50%. For instance, with 2.0%/year in observation arm and 0.4%/year in treatment arm (hazard ratio 0.2) we have 95% power, whereas with 2.5%/year vs. 0.875%/year (hazard ratio 0.35) we have 87% power, and with 1.0% vs. 0.1%/year (hazard ratio 0.1), we have 85% power. Note that under many of these scenarios, there is adequate power even with only 500 patients recruited.

No. Randomised	Base rate/year	0.1	0.2	0.35	0.5
660					
	1.0%	85.2	72.3	49.7	29.5
	2.0%	98.9	95.0	78.6	51.6
	2.5%	99.7	98.1	86.7	60.7
500					
	1.0%	74.4	60.3	39.7	23.5
	2.0%	95.9	88.1	66.8	41.4
	2.5%	98.5	93.9	76.2	49.3

We have also considered the additional power that would come from extended follow-up if the event rate is lower than expected. With 660 patients randomised, an event rate of 1.5%/year in untreated patients and a hazard ratio of 0.35 associated with treatment, the power after 8 years follow-up would be 80.0%.

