2.2. Existing research

Significance of the problem: Anal cancer is a growing problem in the UK and elsewhere. The incidence may be low in the general population (2.0 women and 1.2 men per 100,000 persons of new cancers in 2009) [1] but is rising. In the UK, the number of newly diagnosed cases of anal cancer has increased from 385 women and 211 men in 2001, to 542 and 311 respectively in 2009 [1, 2]. Using a low estimate of completeness, 30% of anal cancer cases may not be registered by the cancer registries [3]. The incidence of anal cancer, however, is more alarming in people with HIV particularly in men who have sex with men (MSM). In HIV-negative MSM, the incidence of anal cancer is 35 per 100,000 person years [4] and is comparable to cervical cancer incidence in

women prior to the introduction of the cervical screening programme in 1988. The incidence in HIV-positive MSM is much higher at 70-100 per 100,000 person years [5]. It is assumed that 3% of the male population are MSM [6], and the Health Protection Agency (HPA) estimates that 35,050 MSM were living with HIV in the UK in 2009 [7]. A meta-analysis showed that the standardised incidence ratio for anal cancer in people with HIV is 28.75 (95% CI 21.6 - 38.3)[8], and some 86,500 people are estimated to be HIV positive in the UK [9]. The risk of anal cancer increases sharply with age [3], particularly for HIV - positive people as a consequence of increased longevity due to Highly Active Antiretroviral Therapy (HAART). Among HIV-positive men in the UK, anal cancer rates have increased from 35 per 100,000 men before the introduction of HAART to 92 per 100,000 men after 1996, and is still on the increase [10,11]. Hence, anal cancer has become a significant cause of morbidity and mortality among HIV-positive people. The economic burden of anal cancer, in terms of the direct medical costs (i.e.- hospitalisation and outpatient costs) and indirect costs (daily allowances charged by taxpayers) is considerable. The management costs of anal cancer is similar to that of cervical cancer, as is the case demonstrated in France, with 38 and 44 million Euros per year, respectively [12]. An effective outpatient based treatment to AIN would help.

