2.4. Research methods

The proposed study is a UK based multi-centre (n \sim 5) two-armed randomised controlled trial involving a total of 660 patients, randomised to receive the intervention (laser ablative treatment) or control (6 monthly observation): 330 in each arm. Eligible patients will be identified from a multi-centre cohort of 12,563 HIV-positive men who have sex with men, attending 5 HIV clinics of the participating centres. Published data suggest the prevalence of high-grade anal neoplasia in these populations to be 30 - 35% [33, 34]. All patients will follow a pre-recruitment screening, recruitment, and randomisation, laser ablative treatment in the treatment arm and observation in the observation arm. All patients will undergo six monthly follow-up, up to a maximum of 5 years (some up to 3 years). The primary outcome will be determined at 72 months.

	Screening	Baseline	6 Wk	6 Mo	12 Mo	24 Mo	30 Mo	36 Mo	42 Mo	48 Mo	54 Mo	60 Mo	66 Mo	72 Mo
Eligibility assessment	\checkmark													
Patient information sheet	\checkmark	\checkmark												
Informed consent		\checkmark												
Allocation		\checkmark												
Demographics + clinical data (CRF 1)		\checkmark												
Questionnaire (QoL, EQ-5D (CRF 2))		\checkmark		\checkmark		\checkmark						\checkmark		
Clinical examination (DRE, HRA)	\checkmark		\checkmark											
Anal cytology (Pap smear)			\checkmark											\checkmark
HPV test			\checkmark											\checkmark
Biopsy for histopathology [¥]	1													\checkmark
Laser ablation (treatment arm only) [#]			1											
Record medication/adverse events				\checkmark		\checkmark	\checkmark							
Record outcome data (CRF 3)				\checkmark										

Table 2: Events at each visit

CRF – case report form; [#]Laser ablation – up to 4 treatment sessions during the whole study period; [¥]Biopsy – Any new/ persistent lesions will be biopsied at each follow-up visits

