Randomisation and allocation: Participants will be randomised, at a ratio of 1:1 once the informed consent has been signed. The next available sequential number will be allocated by the study manager, which then forms the unique identifier for the trial patient. This number will identify all the CRF's for the patient in the study.

Data collection and blinding: Hard copies of baseline documentation will be filed under patients' unique identifier in accordance with DPA agreed practice. The files will not include the patient's personal data or their allocation, which will be stored separately together with the patient's unique id. In all locations, any hard copy patient data will be stored in locked, filing cabinets with access restricted to pre-specified essential users.

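### The power claim rests on observation-arm cancer rates of 1.0-2.5%/year, while the protocol's own incidence and prevalence figures imply at most about 0.2-0.5%/year, and the two are not reconciled

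*Protocol*

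**What the plan says.** Protocol section 2.11: "The total of 660 has been chosen so as to provide 80%-90% power with follow-up until 6 years after the first patient is randomised". The claim is made for several scenarios said to agree with published progression in untreated and minimally treated AIN 2/3, put at about 11% after a median of 5 years. The test is at the "0.05=level using the two-sided log-rank test". The scenarios are: "We consider incidence rates in the surveillance only arm of 1.0%/year, 2.0%/ year and 2.5%/year", crossed with hazard ratios of 0.1, 0.2, 0.35 and 0.5. Below the table, a case for a lower event rate is worked at 1.5%/year with 8 years of follow-up.

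Protocol section 2.2, on the background population: "The incidence in HIV-positive MSM is much higher at 70-100 per 100,000 person years [5". The same section gives 92 per 100,000 for HIV-positive men in the UK after 1996, and says that 30% of anal cancers may go unregistered.

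Protocol section 2.4, on the clinic cohorts from which patients are drawn: "Published data suggest the prevalence of high-grade anal neoplasia in these populations to be 30 - 35% [33, 34".

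**The concern.** Population incidence, prevalence of the precursor and progression among those with the precursor are linked. If about a third of HIV-positive MSM have AIN 2/3, progression among them cannot exceed roughly three times the population incidence. On the protocol's figures that ceiling lies well below the lowest row of the power table. Even the case offered for a lower event rate (1.5%/year) is above that lowest row.

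The primary outcome is anal cancer, analysed by log-rank test at year six. If the lower figures are nearer the truth, only a handful of cancers would be expected by then. A non-significant result would be likely even if laser prevented most cancers, and could be read as evidence of no benefit.

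**Working it through.** **Inputs.** From section 2.11:
- 660 patients, two-sided 0.05 log-rank test, analysis 6 years after the first randomisation.
- Accrual: "we aim to recruit 75 patients in the first 6 months"; "by the end of 12 months, we aim to have recruited a total of 165 patients"; then 400 by year 2 and 660 by year 3.
- Losses of 10% in year 1 and 5% of those remaining in each later year.

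From section 2.4: "Participants will be randomised, at a ratio of 1:1", so 330 per arm. I assume exponential hazards.

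**Step 1: reproduce the plan's table.** Expected events per arm are hazard × person-years under this accrual and loss. Power (Freedman) = Φ(√d × (1−HR)/(1+HR) − 1.96), where d is the total number of events.
- 1.0%/year, HR 0.1: d = 11.97 + 1.22 = 13.19; 3.632 × 0.818 − 1.96 = 1.01; power 84.4% (table 85.2).
- 2.0%/year, HR 0.2: d = 23.44 + 4.85 = 28.29; 5.319 × 0.667 − 1.96 = 1.59; power 94.4% (table 95.0).
- 2.5%/year, HR 0.35: d = 29.0 + 10.5 = 39.5; 6.285 × 0.481 − 1.96 = 1.07; power 85.7% (table 86.7).

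All 24 cells agree within 1.3 points, and the 8-year case gives 79% (stated 80.0). The table is sound given its inputs.

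**Step 2: the rate implied by sections 2.2 and 2.4.** Suppose every cancer arises in men with AIN 2/3. Then progression is at most incidence ÷ prevalence.
- Low: 70 / 0.35 = 200 per 100,000 = 0.20%/year.
- High: 100 / 0.30 = 333 per 100,000 = 0.33%/year.
- With 30% unregistered (divide by 0.70): 0.29 to 0.48%/year.

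The lowest table row, 1.0%/year, is 3 to 5 times the unadjusted ceiling and about twice the most generous one. The cited 11% at 5 years corresponds to −ln(0.89)/5 = 2.3%/year.

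**Step 3: cross-check on counts.** Section 2.2 quotes 35,050 HIV-positive MSM in the UK. At 30-35% prevalence, 2.5%/year implies 35,050 × 0.30 × 0.025 = 263 to 35,050 × 0.35 × 0.025 = 307 cancers a year in this group; 1.0%/year implies 105 to 123. The same section reports 311 cases in all UK men in 2009 (311/0.70 = 444 if 30% were missed). Its own incidence figure implies 35,050 × 70-100 per 100,000, about 25 to 35.

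**Step 4: power at the implied rates.** The method is that of step 1, with 660 patients, year 6 and the stated losses.

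| Observation-arm rate | Observation-arm cancers | HR 0.1 | HR 0.2 | HR 0.35 |
|---|---|---|---|---|
| 0.20%/year | 2.4 | 27% | 21% | 14% |
| 0.33%/year | 4.0 | 41% | 31% | 20% |
| 0.48%/year | 5.8 | 54% | 42% | 27% |

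Example: 0.33%/year over about 1,214 person-years gives 4.05 events, plus 0.41 in the laser arm at HR 0.1; √4.46 × 0.818 − 1.96 = −0.23, power 41%.

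Section 2.11 also expects near-complete registry follow-up. With no losses, HR 0.1 gives 46% at 0.33%/year and 61% at 0.48%/year (6.8 observation-arm cancers).

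**Step 5: rate needed for 80% power at year 6, with the stated losses.** About 0.9%/year (HR 0.1), 1.2%/year (HR 0.2) and 2.1%/year (HR 0.35).

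**Precision.** With so few events every approximation is rough. A Poisson-based log-rank check gives 7% to 41% over 0.20-0.33%/year and all four hazard ratios. Schoenfeld's formula is more optimistic at extreme hazard ratios and passes 80% at 0.48%/year with HR 0.1, but it does not reproduce the protocol's table (98.7 against 85.2 at 1.0%/year, HR 0.1).

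**The case against.** The strongest reply is that section 2.11 states its power conditionally and rests on direct observation of patients with AIN 2/3, which is the relevant population. Section 2.2 adds contemporary progression rates of 13-50% in immunocompromised patients and a historical figure of about 6%, without time spans. The ceiling in step 2 divides an incidence from one source by a prevalence from others. The protocol also says that risk rises sharply with age and that rates are still increasing. Six-monthly anoscopy might bring diagnoses forward. This stands: a reader might infer that the true power is 14-41%, or that 1.0-2.5%/year is wrong, and the documents support neither. They show a conflict, not which side of it is correct.

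A reader might also take the range down to 9%, which is the HR 0.5 result at 0.20%/year. That is not a fair comparison, because the protocol's own table shows only 29.5-60.7% at HR 0.5 with 660 patients and never claims adequacy there.

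The protocol does have some cushion: the 8-year case in section 2.11, five further years of passive follow-up in section 2.12 and a ten-year cancer outcome in section 2.13. This counts in its favour, but the 8-year case is worked at 1.5%/year. At HR 0.35 without losses, 8 years gives about 31% at 0.33%/year and 42% at 0.48%/year.

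**Conclusion.** The concern holds as an unreconciled conflict of assumptions, not as a calculation error. The protocol's incidence and prevalence figures cap observation-arm progression at about 0.20-0.33%/year, or 0.48%/year with its own under-registration figure. Every rate used to justify 660 patients is at least about twice the highest of these. At the implied rates, year-6 power for the hazard ratios the protocol presents as adequate would be 14-41%, rising to at most 54% at 0.48%/year and 61% with complete registry follow-up as well. About 2 to 7 observation-arm cancers would be expected, against 12 to 29 in the table's scenarios.

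This rests on three assumptions: all cancers arise from AIN 2/3 (which makes the rate a ceiling), the quoted incidence and prevalence apply to the same population, and trial patients resemble the men with AIN 2/3 in the screened clinics.

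**What to change.** 1. In section 2.11, reconcile the 11% progression figure with the incidence in section 2.2 and the prevalence in section 2.4, stating why trial patients should progress faster if that is the belief.
2. Add rows at about 0.2, 0.33 and 0.5%/year to the power table.
3. Restate the claim: 80% power at year 6 requires observation-arm incidence of at least about 0.9%/year (HR 0.1), 1.2%/year (HR 0.2) or 2.1%/year (HR 0.35), and power is well below 80% at the rates implied by sections 2.2 and 2.4.
4. State in advance that a non-significant year-6 result with few cancers is not evidence of no benefit, and that the passive follow-up analysis already planned will be used if the blinded pooled cancer count is low.

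I would not tie item 4 to the event count needed for 80% power at HR 0.35, which is about 34. At the upper implied rates (0.33-0.48%/year) only about 14 to 20 cancers in total would be expected by year 11 at that hazard ratio, even without losses.

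The cost is a less favourable power statement and a pooled count from data already collected. No extra patients are needed.

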2.12. Statistical analysis

The proposed study seeks to measure the long-term (5-6 year) clinical effect and cost-effectiveness of laser ablative therapy of AIN 2/3 on incidence of anal cancer in HIV-positive MSM. Participants will be examined 6-12 monthly for up to 6 years. In addition to active follow-up during the study, there will be further follow-up, passively, for 5 more years upon completion of the study. For this, participants will be asked to consent to flagging in the national cancer registry.

The trial is divided into three phases so that substantial resources are not committed in the unlikely event that we are unable to recruit or follow-up patients. Thus the primary outcome of phase I is the numbers recruited in the first six months, and the primary outcomes of phase II are the compliance with the 6 month follow-up visit and the continued recruitment in the second six months.

PRIMARY OUTCOME MEASURE:

1. Incidence of anal cancer in HIV-positive MSM after treatment with laser, compared to incidence of anal cancer in an observed group [to be analysed at the end of year six using the log-rank test].

SECONDARY OUTCOME MEASURES:

2. Proportion of patients with clearance of AIN 2/3 lesions in the treated group, compared to proportion in the untreated group, and to measure this difference for low- (1-2 quadrants) and high-volume (3-4 quadrants) AIN 2/3 disease [Time frame: 1, 3 and 5 years after randomisation].

3. Number of treatment attempts necessary to clear AIN 2/3 lesions, and the difference between low- and high-volume disease [Time frame: 1, 3 and 5 years after first treatment].

4. Incidence of metachronous (new) lesions and the rate of recurrence of AIN 2/3 disease after clearance [[Time frame: 1, 3 and 5 years after randomisation].

5. Adherence and drop-out rates of participants undergoing this treatment regime, compared to those undergoing observation [Time frame: through 6 years].

6. Correlation of viral loads, CD4 cell count and lesion size with a) clinical response (progression, persistence, regression) of AIN 2/3 and b) treatment effectiveness or failure.

7. Correlation of high-risk HPV types with a) clearance of AIN 2/3 after treatment, and b) progression of disease to anal cancer.

8. Quality of life in HIV-positive MSM with AIN 2/3 undergoing treatment with laser therapy, compared to quality of life with a watch and wait approach (observation).

9. Differences in psychological outcomes (anxiety, depression, sexual function, cancer fear), between the treatment and surveillance arms.

10. Intervention costs of laser ablative therapy in HIV-positive MSM with AIN 2/3 lesions to prevent anal cancer.

11. NHS treatment costs related to anal neoplasia and cancer in both intervention and control arms.

The primary outcome will be assessed using the log-rank test based on an intention to treat analysis of all randomised patients. Assuming passive follow-up is complete; patients will be censored at death or emigration but not otherwise. Analysis of active follow-up will be censored at the last visit of each patient. If some patients in the surveillance only arm receive excisional or ablative treatment for their AIN (prior to the development of cancer) we will also use methods appropriate for the estimation of the treatment effect in randomised controlled trials with non-compliance.

The data will be held in a secure database. A detailed statistical analysis plan will be written and independently reviewed before the statistician is given access to any un-blinded data.

An annual statistical report will be written based on an agreed format for the data monitoring committee. Two versions will be made: one for the independent members of the Data Monitoring Committee and a redacted version for the non-independent members of the committee.

A formal interim analysis has not been planned because the power to observe a significant result with alpha of 0.002 (two-sided) after four years is low even under extremes of what is reasonable in the two arms. Thus for instance, with 2.5%/year in the surveillance arm and 0.25%/year in the treated arm, there would be 69% power. Were one to obtain a p-value of less than 0.002 at year 4, it would be up to the data monitoring committee to make a recommendation regarding early stopping and the offering of treatment to all patients in the surveillance arm.

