We plan to start recruitment to the study in February 2015. We will advertise and recruit a trial co-ordinator and advertise the study in the relevant media. We will set up the screening and recruitment clinics at Barts Health NHS Trust and at University College London/ Royal Free hospital. First patient randomisation will start by 2nd February 2015. Recruitment will continue to reach the 1st target of 75 patients by 1st November 2015. The first funding decision point is reached on 2nd November 2015. Recruitment continued till the second decision point on 1st May 2016, to recruit a minimum of 165 patients into the trial. Thereafter, on agreement, recruitment continued, till 1st February 2017, when 400 patients are randomised into the study. After 1st May 2016, trial screening and case detection for the trial extended to 3 other centres where large HIV positive patient cohorts attend, so as to recruit a total of 400 cases into the study. 1st February 2017 will mark the completion of recruit a total of 660 participants (a further 260 patients) to the trial. Participants attend every six months since recruitment, and the study ends on 31st January 2021. Statistical analysis, research evaluation, and publication of results will occur over the following three months. The project milestones and Gantt chart of the project are shown below.

	Start date	Finish date
Contract start date	1/10/2014	
Trial set-up		
Trial co-ordinator recruitment	30/6/2014	1/10/2014
Trial document development and IRAS	25/8/2014	3/10/2014

form completion			
Database development and testing		3/10/2014	1/1/2015
Ethics application		6/11/2014	24/12/2014
NHS approval		29/12/2014	30/1/2015
Site agreements		29/12/2014	30/1/2014
Feasibility study			
1 st patient recruitment	22/2/2015		
1 patient recruitment	23/2/2015		
Phase I	0 -9 months (allowing lead-in period)	24/2/2015	23/11/2015
Target for recruitment	75		
Phase II	9 – 15 months	24/11/2015	24/5/2016
Target for recruitment	165 (inclusive of Phase I recruitment)		
Main Trial			
Phase III	15 – 24 months	25/5/2016	23/2/2017
Target for recruitment	400 (inclusive of phase I and II recruitment)		
Phase IV	24 – 36 months	24/2/2017	23/2/2018
Target for recruitment	660 (inclusive of Phase I, II, III recruitment)		
Last patient recruitment	23/2/2018		
Last patient's last visit	25/2/2021		

4. Service users

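### The primary analysis keeps clinic drop-outs at risk on an assumption of complete registry capture that the protocol does not reconcile with its own background figure, and the printed power belongs to a different censoring rule

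*Protocol*

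**What the plan says.** All of this is in the protocol.

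- **Primary test (2.12):** "The primary outcome will be assessed using the log-rank test based on an intention to treat analysis of all randomised patients".
- **Censoring (2.12):** "Assuming passive follow-up is complete; patients will be censored at death or emigration but not otherwise". The next sentence adds: "Analysis of active follow-up will be censored at the last visit of each patient". It does not say whether that second analysis is a sensitivity analysis or a fallback.
- **Expected capture (2.11):** "We anticipate close to 100% passive follow-up for anal cancer though flagging with the English Cancer Registry". The same paragraph sets losses of 10% in year 1 and 5% of those remaining in each later year, and explains that these are people who stop attending clinic.
- **Registration in general (2.2):** "Using a low estimate of completeness, 30% of anal cancer cases may not be registered by the cancer registries".
- **Basis for flagging (2.12):** "participants will be asked to consent to flagging in the national cancer registry".
- **Timing (3, Project timetable and milestones), after the study end date:** "Statistical analysis, research evaluation, and publication of results will occur over the following three months".
- **Power (2.11):** with 660 randomised, 86.7% at 2.5%/year and hazard ratio 0.35, and 78.6% at 2.0%/year and 0.35.

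**The concern.** Under the primary rule, a cancer in someone still attending can be found at a study visit. A cancer in someone who has left can be found only through the registry. If the registry misses it, or has not yet processed it when the data are cut, that person contributes event-free time that nobody observed. Someone who has left and did not agree to flagging has no stated route by which a cancer would be found, yet the rule still keeps them at risk.

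The rule rests on near-complete capture, while the background section cites a figure that, taken at face value, points the other way. No check or threshold is given for deciding whether passive follow-up was complete.

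There is a second mismatch. The sample size section removes people at clinic loss, whereas the primary analysis does not. A reader cannot tell which analysis the printed power describes.

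At stake are the number of events that count in a trial expecting only some tens of cancers and, if drop-out differed between arms, the size of the estimated effect.

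**Working it through.** **Inputs from the protocol.** 330 per arm. Cumulative accrual 75, 165, 400 and 660 at 0.5, 1, 2 and 3 years. Analysis at year 6. Two-sided 0.05. Clinic loss 10% in year 1, then 5% per year. Non-registration 30% (2.2).

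**Assumptions added here.** Constant hazards. Linear accrual between milestones. The 30% applies only to cancers after clinic loss.

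**Formula.** Freedman: power = Φ(√d × (1 − HR)/(1 + HR) − 1.96), where d is expected events.

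**Step 1: reproduce the table.** Censoring at clinic loss:

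- 2.5%/0.35: d = 29.0 + 10.5 = 39.5. √39.5 × 0.65/1.35 − 1.96 = 1.07, giving 85.7% (printed 86.7%).
- 2.0%/0.35: d = 23.4 + 8.4 = 31.9 before rounding, giving 77.6% (printed 78.6%).
- All 24 printed cells are matched to within 1.2 points.

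**Step 2: power under the primary rule with complete capture.**

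| Scenario | Events before drop-out | Events after | Total | Power | Printed |
|---|---|---|---|---|---|
| 2.5%/0.35 | 39.5 | 6.8 | 46.3 | 90.6% | 86.7% |
| 2.0%/0.35 | 31.9 | 5.5 | 37.3 | 83.7% | 78.6% |

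The printed values are 3.9 and 5.1 points lower, so the table belongs to censoring at clinic loss.

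**Step 3: share that depends on the registry.** 6.8/46.3 = 14.6% and 5.5/37.3 = 14.7%. About 24% of participants have left clinic by the analysis.

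**Step 4: 30% unregistered, equal losses.** 0.30 × 14.6% = 4.4% of events (2.0 of 46.3, or 1.6 of 37.3). The event ratio stays at 0.363 and 0.360. Power goes from 90.6% to 89.3% and from 83.7% to 82.0%, both still above the printed values.

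**Step 5: registry delay.** The protocol gives no figure. If capture stopped 6 or 12 months before the cut (assumed), lost events would rise from 4.4% to 6.2% or 7.8%. With equal losses the event ratio stays at about 0.36.

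**Step 6: unequal losses (assumed).** Observation arm 20% then 10% per year, laser arm as stated, at 2.5%/0.35.

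- Registry-only share: observation 9.35/33.94 = 27.5%, laser 1.81/12.32 = 14.7%.
- Event ratio with 30% missed: 0.363 × (1 − 0.30 × 0.147)/(1 − 0.30 × 0.275) = 0.378.
- On the log scale the shift is ln(0.378/0.363) = 0.04. The standard error is about √(1/33.9 + 1/12.3) = 0.33, so the shift is about an eighth of a standard error.
- Power computed at the event ratio falls from 88.9% to 84.0%.

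**The case against.** The strongest reply is that most of this is already handled.

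- The rule is conditional on complete passive follow-up, and an analysis censored at the last visit is already planned. This stands in part. The protocol still does not say how completeness will be judged or what role the second analysis has.
- The 30% is a low-completeness background figure for registration of anal cancer in general. It is not a figure for individually flagged trial participants. This stands, so 30% serves here as an upper bound for a sensitivity analysis and not as an expected loss.
- The power table is conservative for the primary analysis and fits the active follow-up analysis. This also stands. The complaint is about labelling, not a shortage of patients.
- Registry cut-off dates often belong in an analysis plan. That is fair as to detail, but here the protocol itself fixes the rule and excludes any other reason for censoring.

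Three stronger readings are tempting and are not supported.

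- **That the observation arm will leave more.** Section 2.7 says only that its patients may press for treatment or seek it elsewhere. It gives no comparative retention, and 2.11 uses one loss rate for everyone.
- **That leavers simply count as cancer-free.** Registered cancers do count.
- **That incidence in the passive extension is understated by 30%.** That applies the low-completeness figure as if it were the expected one. Cumulative incidence also includes cancers already found in clinic.

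**Conclusion.** The point holds in a limited form. The protocol relies on near-complete registry capture for its primary analysis, cites a background figure at odds with that, and does not reconcile the two. The rule also credits drop-outs with event-free time that the registry may not yet cover at the data cut.

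The printed power describes censoring at clinic loss. For the primary rule with complete capture, power is about 91% and 84% in the two scenarios shown, against 86.7% and 78.6% printed.

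The numerical harm is modest. With the stated equal losses, about 4.4% of events go missing at worst-case registration, the hazard ratio is practically unchanged, and power falls by 1.3 to 1.7 points while staying above the table. A shift in the effect estimate, from about 0.36 to 0.38, needs unequal drop-out, which is an assumption made here. These results rest on constant hazards, on the accrual shape between milestones, and on drop-outs having the same cancer risk as attenders.

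**What to change.** 1. Censor registry-only participants at the date to which the registry declares its data complete, and censor those without flagging consent at their last visit.
2. Name the planned analysis censored at last visit as the sensitivity analysis to the primary one. Add a second that puts 0 to 30% missed cancers into registry-only time, separately by arm. The second is needed because a completeness date deals with delay but not with cancers that are never registered.
3. Label the power table as applying to censoring at clinic loss, and state the power for the primary rule beside it.
4. Reconcile the capture expected in 2.11 with the figure in 2.2, for instance by explaining why flagged participants should differ from registration in general.

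The cost is wording, one extra analysis, and slightly less person-time for drop-outs. No added patients or visits are needed.
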